**Figure 1. Schematic diagram for retrospective cohort study with risk-set sampling for convalescent plasma exposure**

CP= convalescent plasma

\* Hospital admission includes the earliest encounters at emergency or inpatient departments around COVID-19 confirmation within  $\pm 14$  days.

† The earliest possible date is July 1st, 2020.

Step-by-step risk-set sampling with replacement for the retrospective cohort design to account for confounding and to strategize EHR abstraction at BSWH:

1. Identify patients hospitalized with laboratory-confirmed COVID-19 (Source population)

The study population will be patients with laboratory-confirmed COVID-19 (i.e., RT-PCR test results recorded by the BSWH laboratory informatics systems and/or the EHR system) and received or matched to a patient who received convalescent plasma from July 1st to September 28th. Patients must have at least 28 days of observation opportunity from the date of data pull to the index date (reverse order). Patients cannot have been previously admitted into hospitals due to RT-PCR laboratory confirmed COVID-19.

2. Identify patients who received convalescent plasma (Exposed group)

Blood bank records will be scanned to identify patients who had at least one order to transfuse COVID-19 convalescent plasma using the International Society of Blood Transfusion (ISBT) 128 codes (Appendix 1). The order will be linked to the administration record of the plasma to determine the date and time the product was given.

3. Risk-set sampling and matching variables (Unexposed group)

For each patient who received a first dose of convalescent plasma, we will sample from the source population who did not receive convalescent plasma (Unexposed group) at the same calendar time ( $\pm 2$  days) and match on the following variables. One patient could be sampled at maximum twice; first sampled into the unexposed group and later sampled into the exposed group due to initiation of convalescent plasma transfusion during follow-up.

- Calendar date around the index date within  $\pm 2$  days: Risk-set sampling to match exposed and unexposed patients will account for this factor
- Age ( $\pm 5$  years)
- Sex (female, male)
- Days from hospital admission to the index date

4. Propensity score matching and baseline covariates

The propensity score is defined as the probability of a patient receiving convalescent plasma conditioned on their observed baseline covariates. Baseline is defined as the period prior to and including the index date. Baseline covariates for the propensity score modeling is listed below and further defined in Appendix 2. To account for confounding by baseline covariates described below, a logistic regression will be fitted to estimate the probability of receiving convalescent plasma. In the event of low frequency of certain covariates, that may cause model convergence problem, such covariates will be removed from the propensity score model. Covariates that are strongly related to convalescent plasma transfusion but only weakly related to the primary outcome will not be included in the propensity model to preserve precision of the estimates. Exposed and unexposed patients will be matched according to propensity score with nearest neighbor caliper matching algorithm without replacement with a match ratio up to 1:4 based on the power calculation (Section V. Sample Size). Propensity density plots pre- and post-matching will be evaluated for overlapping areas.

- Age (continuous)
- Race and ethnicity
- Hospital site
- Comorbidities
- Concomitant medications
- Oxygen requirements as a proxy for disease severity (Appendix 3) 4-12 hours prior to the index date

- Laboratory results: creatinine, D-dimer, troponin, absolute lymphocyte count, ferritin, C-reactive protein
- Vital signs: Respiratory rate (min), Heart rate (min), Systolic BP (mmHg), Temperature (°C)

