### Exposure

COVID-19 convalescent plasma will be identified with ISBT-128 code (Appendix 1) in local Blood Bank data. First exposure to convalescent plasma is of interest for patients who received multiple doses. Patients can receive convalescent plasma any time during the hospital stay associated with the COVID-19 diagnosis.

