### Secondary Analyses

- 1) If sample size allows, stratify analyses by mechanical ventilator use prior to or at the index date
- 2) If sample size allows, subgroup analyses comparing patients who received convalescent plasma and remdesivir, with those who only received remdesivir.
- 3) If sample size allows, stratify analyses by time interval from hospital admission to the index date (<72 hours vs. ≥72 hours).
- 4) If sample size allows, stratify analyses by disease severity measured by oxygenation.

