### Sensitivity Analyses

- 1) To assess the COVID-19 cohort definition of hospital admission within ±14 days of laboratory confirmed COVID-19 diagnosis, we will further restrict the source population to those who were admitted into affiliated BSWH hospitals within ±7 days of laboratory confirmed COVID-19 diagnosis. This is because COVID-19 could progress quickly and patients could also transfer to hospitals outside of the network of BSWH with a large time window around COVID-19

confirmation resulting in potential residual confounding by severity and survivor bias by prior treatment

- 2) Instead of ending the observation period at 28 days since the index date, we will continue follow-up until the end of the study period, unless an outcome event occurs earlier. Patients will be followed from the index date until the earliest of the following: 1) death, 2) discharge alive, 3) the end of the study period, or 4) the date of unexposed patients who were administrated COVID-19 convalescent plasma.
- 3) Given that mortality data after hospital discharge is limited and that patients could be discharged for palliative care due to disease worsening, the outcome “discharge alive” will be considered a competing risk for 28-day in-hospital mortality. To account for competing risk of in-hospital death and discharge alive, sub-distribution hazard ratios will be estimated from the Fine-Gray model. Cumulative incidence function will be estimated by modeling the cause-specific hazard function of all causes.

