### Appendix 3. Oxygen requirements as a proxy for disease severity (listed from lowest to highest disease severity)

- Room air
  - No documentation of the other categories listed below
- Basic oxygenation
  - Includes: Simple face mask, nasal cannula, CPAP/Bubble CPAP, T-piece, blow by, nasal prongs, open oxygen mask, tracheostomy collar, venturi mask system (if FiO2 % is < 45%), face tent (if FiO2 % is < 45%; up to 6L), nasal cannula with reservoir (i.e. oximizer; if FiO2 % is < 45%; up to 6L)
- Advanced oxygenation
  - Includes: High flow nasal cannula (HFNC), BiPAP/NPPV/NIV, Vapotherm, blender system, high flow mask, manual resuscitator, non-rebreather mask (NRB), Oxyhood, partial rebreather mask, venturi mask system (if FiO2 % is ≥ 45%), face tent (if FiO2 % is ≥ 45%; ≥ 7L), nasal cannula with reservoir (i.e. oximizer; if FiO2 % is ≥ 45%; ≥ 7L)
- Invasive ventilation
  - Transtracheal catheter, Invasive mechanical ventilation vent mode
    - CPT code 94002 (mechanical ventilation for initial day), 94003 (subsequent day), 94004 (per day)
- ECMO

NOTE: In cases where clinical flow sheets do not contain sufficient information to classify the level of oxygen support, categorization will be based on clinician review of the electronic health record

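### The sampling rule for unexposed patients does not require the positive RT-PCR to be on or before the index date, and the definition of admission can misdate a matching variable in either arm

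*Protocol*

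**What the plan says.** Protocol, Section III, Cohort Sampling, step 1 takes as source population hospitalised patients with laboratory-confirmed COVID-19, with at least 28 days of possible observation and no earlier COVID-19 admission. Step 3 then states: "we will sample from the source population who did not receive convalescent plasma (Unexposed group) at the same calendar time", within 2 days either way. The matching variables are calendar date, age within 5 years, sex, and "Days from hospital admission to the index date".

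The footnote to Figure 1 defines admission: "Hospital admission includes the earliest encounters at emergency or inpatient departments around COVID-19 confirmation within" 14 days either way. Sensitivity analysis 1 in Section IV describes the same cohort definition as "hospital admission within ±14 days of laboratory confirmed COVID-19 diagnosis" and tightens it to 7 days. Secondary analysis 3 will "stratify analyses by time interval from hospital admission to the index date", cut at 72 hours.

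For exposed patients, the Exposure section says: "Patients can receive convalescent plasma any time during the hospital stay associated with the COVID-19 diagnosis".

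**The concern.** A risk set should hold only patients who could have been given plasma on that day. For a COVID-19 treatment, that means patients already known to be infected and in hospital. Step 1 requires hospitalisation and confirmation, but it does not date either of them against the index date, and step 3 adds no such condition.

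A patient admitted for another reason who tests positive some days later meets the rule as written on any day before the test. That patient is selected on a future event. Someone with the same admission who died before being tested never enters the source population. The time between index date and test is therefore free of deaths by construction.

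The second issue concerns dating. If the earliest encounter in the window is an ED visit from which the patient went home, days from admission count from that visit and not from the stay in which the patient is analysed. That count is a matching variable and also defines the 72-hour strata.

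**Working it through.** **1. Can a comparator be sampled before the positive test?** Set the admission day to 0, the day of the positive test to P and the index day to d. The cohort definition allows P from 0 to 14 when the test follows admission. Step 3 places no condition linking d to P, so any d < P is allowed. Example: admitted day 0, positive on day 8, sampled on day 3. The patient satisfies step 1 and can be matched on date, age, sex and three days from admission.

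**2. How long is the guaranteed survival?** It lasts P − d days, which is at most 14 − d.
- In the example: 8 − 3 = 5 days.
- At the extreme (d = 0, P = 14): 14 days, or 14/28 = 50% of primary follow-up.
- Under the 7-day sensitivity analysis: at most 7 days, or 7/28 = 25%. The window is shorter, but the missing condition is the same.

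These are maxima permitted by the text, not expected values. An exposed patient is identified by the transfusion itself, given in the stay associated with the diagnosis, so the problem falls on the unexposed side.

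**3. What would ED dating do?** An ED visit that ended in discharge three days before the analysed stay adds 3 × 24 = 72 hours. An index date on the first day of that stay would then be counted at 72 hours or more, not under 72. The footnote makes no distinction between exposed and unexposed patients, so the error can arise in both.

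**4. Is there a size?** The only relevant planning figure is the 28-day survival of 0.75 in Section V, a risk of 0.25. As a check that this is the risk behind Table 1, take the row with 1,500 patients at 1:4 (stated ratio 0.68), using the Freedman log-rank formula, two-sided 0.05 and 80% power. With ratio 0.684:
- exposed risk = 0.25 × 0.684 = 0.171
- HR = ln(0.829)/ln(0.75) = 0.652
- events = 7.849 × 4 × (1 + 0.652/4)² / (1 − 0.652)² ≈ 351
- mean risk = (0.171 + 4 × 0.25)/5 = 0.2342
- N ≈ 351/0.2342 ≈ 1,500

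All 16 rows reproduce in this way. Nothing in Table 1 depends on the sampling rule, and no sample-size figure needs to change.

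The document gives neither the share f of comparators sampled before diagnosis nor their mortality relative to the others, r. By assumption only, and before propensity matching:

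unexposed risk = 0.25 × [1 − f(1 − r)]; apparent risk ratio under no effect = 1/[1 − f(1 − r)]

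| Assumed f | Assumed r | Unexposed risk | Apparent ratio when the truth is 1.00 |
|---|---|---|---|
| 5% | 0.6 | 0.245 | 1.02 |
| 15% | 0.3 | 0.224 | 1.12 |
| 5% | 1.4 | 0.255 | 0.98 |
| 15% | 1.7 | 0.276 | 0.905 |

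The last two rows mirror the first two, with the 40% and 70% deficits in mortality turned into excesses of the same size. The sign depends entirely on whether r is below or above 1, and the document does not settle that.

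**The case against.** The strongest reply is that the primary Cox model uses the propensity-matched cohort, not the raw risk set. The score includes remdesivir, steroids, IL-6 inhibitors, inflammatory markers, vital signs and oxygen support 4 to 12 hours before the index date. A patient not yet suspected of COVID-19 would seldom have COVID-directed drugs, would tend to a low score, and would often fail the caliper. Covariates left with a standardised difference above 0.1 enter the model. This stands as mitigation: fewer such comparators reach the primary analysis. It is not an eligibility rule. The score contains neither diagnosis status nor time since the test, and it cannot undo selection on a later test. Oxygen support is a weak screen, because the room-air category is assigned on "No documentation of the other categories listed below".

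The drawing in Figure 1 was also not available for this review, and it may show confirmation before the index date. If so, step 3 should still say it, since step 3 is the rule that will be programmed.

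A reader might go further and infer that the plan lacks the two criteria altogether. It does not: step 1 requires hospitalisation and confirmation at some point, and what is missing is their timing.

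A reader might also infer that patients at home serve as comparators. The text gives little support for this. Primary follow-up ends at discharge alive and the outcome is in-hospital death, so a patient already sent home would have no follow-up and would largely drop out. Step 1 also bars earlier COVID-19 admissions, and if an ED encounter counts as admission, some PCR-positive ED visits are arguably excluded already. What remains of the ED route is the misdating of admission.

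**Conclusion.** The concern holds in a limited form. As written, a comparator may be sampled before the positive test, and the sampling rule then guarantees survival from index date to test on the unexposed side. The 7-day sensitivity analysis and propensity matching reduce this without removing it. The earliest-encounter definition can separately misdate days from admission and the 72-hour strata, in both arms.

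The size and net direction of the bias cannot be determined. It is tempting to conclude that comparators would be less ill and that plasma would look worse by 2% to 12%. That range rests on assumed shares and on relative mortality set below 1, and it ignores propensity matching. Patients who were in hospital for another reason and tested positive later may be sicker, which would reverse the effect of their risk level. The guaranteed survival taken alone favours the unexposed group, but that does not fix the net sign.

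The conclusion rests on the visible wording of step 1, step 3, the Figure 1 footnote and sensitivity analysis 1. It is a worthwhile, inexpensive correction to a stated sampling rule, not evidence that the primary result would be wrong.

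**What to change.** In step 3 of Cohort Sampling, add that on the index date each sampled patient must (a) have a positive RT-PCR dated on or before that date and (b) be in hospital in the stay being analysed.

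In the Figure 1 footnote, date admission in both arms from the ED or inpatient encounter that runs without discharge into that stay. Use the same date for the days-from-admission match and for the 72-hour strata.

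This takes a few sentences and relies on test, encounter and discharge dates that the cohort definition and follow-up already need. The downside is a slightly smaller pool of comparators.

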### Cohort Sampling

This is a retrospective cohort study with risk-set sampling for exposure status of convalescent plasma using EHRs in the Baylor Scott & White Health (BSWH) healthcare delivery system. In brief, patients who received convalescent plasma will be matched to a similar population who did not receive convalescent plasma around the same time ( $\pm 2$  days) of transfusion across sites. The administration date of convalescent plasma for the treated population and the matched date for the untreated population are thereafter referred as the index date. The matching scheme for risk-set sampling is defined in step-by-

step points in the following paragraph. The follow-up for the matched cohort will start from the index date and continue until the end of the observation period. The observation period for this study is defined as at least 28 days from the index date. In other words, the index date must be at least 28 days prior to the date of data pull to allow for adequate follow-up and minimize selection bias from informative censoring due to death or discharge for palliative care. An unexposed patient at the index date could receive convalescent plasma during the follow-up and the follow-up will be censored at the administration date of convalescent plasma (Figure 1).

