#### Comparative Analyses

A Kaplan-Meier curve will be plotted using the propensity score matched cohorts. To control for measured confounding, patients will be sampled in risk sets with replacement and propensity score matched. Distribution of covariates between exposure groups before and after propensity score matching will be assessed to evaluate the balance of baseline covariates and potential residual confounding. Absolute standardized differences, the differences in means or proportions divided by the pooled standard deviation, will be computed for each covariate to check its distribution balance within exposure groups. Covariates with an absolute standard difference greater than 0.1 will be further controlled in the analyses by including specific variables in the Cox model.

The adjusted incidence rates of death in the first 7, 14, 21, and 28 days after the index date will be estimated for the exposed and unexposed groups using the propensity score-matched cohort.

For the primary outcome (28-day in-hospital mortality), a Cox proportional hazards regression will estimate hazards ratios (HRs) and 95% confidence intervals (CIs) using the propensity score-matched cohort. Patients will be followed from the index date until the earliest of the following: 1) death, 2) discharge alive, 3) day 28 since the index date, or 4) the date of unexposed patients who were administered COVID-19 convalescent plasma. Patients discharged alive will be censored at the discharge date. The proportional hazards assumption will be evaluated using Schoenfeld residuals test and visual inspection of log-log plots.

For the secondary outcome of discharge alive, we will not censor the follow-up at the date of in-hospital death but will censor at day 28 to account for this worst possible outcome and to account for the competing risk of in-hospital death. In other words, patients will be followed from the index date until the earliest of the following: 1) discharge alive, 2) day 28 since the index date, or 3) the date of unexposed patients who were administered COVID-19 convalescent plasma.

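### The sampling rule lets a comparator be indexed before the first positive RT-PCR, which can push the mortality hazard ratio against plasma by an amount the protocol does not let one fix

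*Protocol*

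**What the plan says.** All of this is in the Protocol.

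- **Source population** (Section III, Cohort Sampling, step 1): hospitalised patients with RT-PCR-confirmed COVID-19. No time is set by which confirmation must have occurred.
- **Admission** (Figure 1 footnote): "Hospital admission includes the earliest encounters at emergency or inpatient departments around COVID-19 confirmation within" 14 days on either side. Sensitivity analysis 1 restates the cohort definition as "hospital admission within ±14 days of laboratory confirmed COVID-19 diagnosis".
- **Comparators** (step 3): "we will sample from the source population who did not receive convalescent plasma (Unexposed group) at the same calendar time", give or take 2 days. They are also matched on age, sex and "Days from hospital admission to the index date".
- **Recipients** (Exposure): "Patients can receive convalescent plasma any time during the hospital stay associated with the COVID-19 diagnosis". Confirmation before transfusion is not stated here either.
- **Follow-up** (Cohort Sampling): "The follow-up for the matched cohort will start from the index date". For the primary outcome it ends at death, or at "2) discharge alive, 3) day 28 since the index date", or when a comparator receives plasma (Comparative Analyses).

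Neither the matching variables nor the propensity covariates in Appendix 2 include time since confirmation.

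**The concern.** The clock used for sampling is admission, while membership of the source population depends on the RT-PCR result, and the footnote lets the result follow admission. Take a patient admitted on day 0 and first positive on day 10. As the text stands, that patient can be drawn as a comparator on day 2. Had the patient died on day 6 untested, there would have been no such comparator. Entry therefore depends on something that happens after index, and the days from index to test are normally free of death by construction.

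A covariate cannot put back deaths that the entry rule has excluded. If recipients are mostly confirmed before they are transfused, the comparator death rate is too low, and the primary hazard ratio moves towards or above 1. Some of these comparators may also not have been infected at index.

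**Working it through.** **The plan's own figure.** Table 1 (Section V) reproduces. With background 28-day risk 0.25 and risk ratio 0.709, HR = ln(1 − 0.25 × 0.709)/ln(0.75) = 0.678. The Freedman log-rank formula at 1:1 gives events = 7.849 × (1.678/0.322)² ≈ 213. Dividing by the mean risk (0.25 + 0.177)/2 gives about 1,000 patients, against a tabulated ratio of 0.71 for 1,000. All 16 rows agree to two decimals. The table does not bear on eligibility; it supplies only a planning risk (25%) and a target effect (0.7).

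**Inputs for the bias**
- From the protocol: 28 days of follow-up, and a lag from index to test of at most 14 days (7 in sensitivity analysis 1).
- Assumed, because not given: the share *f* of comparators unconfirmed at index; daily death hazard 0.015; daily discharge hazard 0.08; lag uniform over 1-7 or 1-14 days; all recipients confirmed at index; no plasma effect.

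**Main model, in daily steps**
1. Confirmed patient: in-hospital days = (1 − 0.905²⁸)/0.095 = 9.883; deaths = 0.015 × 9.883 = 0.1482 (28-day risk 15%).
2. Late-tested comparator: death hazard zero until the test, discharge unchanged. Averaged over lags 1-7: 0.1044 deaths in 10.379 days. Over lags 1-14: 0.0784 deaths in 10.654 days.
3. If the stay ends before the test: no in-hospital death, and (1 − 0.92²⁸)/0.08 = 11.289 days.
4. HR = 0.015 ÷ {[(1 − f) × 0.1482 + f × deaths]/[(1 − f) × 9.883 + f × days]}.

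Example, *f* = 10%, lags 1-14: deaths 0.1334 + 0.0078 = 0.1413; days 8.895 + 1.065 = 9.960; rate 0.01418; HR = 1.06.

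| Share *f* | Lags 1-7 | Lags 1-14 | Stay ended before test |
|---|---|---|---|
| 2% | 1.01 | 1.01 | 1.02 |
| 5% | 1.02 | 1.03 | 1.06 |
| 10% | 1.04 | 1.06 | 1.13 |
| 15% | 1.05 | 1.09 | 1.20 |

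**Cross-check by a second method.** The expected Cox score equation was solved at 1:3 with the protocol's 25% risk (death hazard −ln 0.75/28 = 0.01027 per day) and one fixed lag for every late-tested comparator, with neither death nor discharge before the test.

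| True HR | Discharge per day | *f* | Lag 2 | Lag 7 | Lag 14 |
|---|---|---|---|---|---|
| 1.00 | 0 | 5% | 1.004 | 1.015 | 1.029 |
| 1.00 | 0 | 10% | 1.008 | 1.029 | 1.061 |
| 1.00 | 0.08 | 5% | 1.010 | 1.035 | 1.070 |
| 1.00 | 0.08 | 10% | 1.020 | 1.070 | 1.143 |
| 0.70 | 0.08 | 10% | 0.714 | 0.749 | 0.799 |

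The direction is the same throughout. Short lags do little; a fixed 14-day lag is the extreme that the window allows.

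**Discharge alive.** If the later test falls in the same stay, the comparator cannot be discharged before it either. In the daily model this gives 0.7638 discharges in 13.548 days (lags 1-7) or 0.7243 in 16.553 (lags 1-14), against 0.7906 in 9.883. At *f* = 10% the rates are (0.7116 + 0.0764)/(8.895 + 1.355) = 0.0769 and (0.7116 + 0.0724)/(8.895 + 1.655) = 0.0743. The ratios are 0.08/0.0769 = 1.04 and 0.08/0.0743 = 1.08, in plasma's favour. The size is approximate, because the plan keeps deaths under observation to day 28. The direction stands, since discharges are both later and fewer.

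**The case against.** **The text is silent, not explicit.** Sampling risk sets from a laboratory-confirmed population can fairly be read as meaning confirmed by that date, and the Figure 1 drawing, not available here, may show that order. This stands against any claim that the estimate is certainly biased. It does not remove the gap: the protocol lists its sampling conditions step by step and omits this one, while the footnote permits admission before confirmation.

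**Propensity matching will thin out such pairs.** Oxygen support, remdesivir, dexamethasone and inflammatory markers make a patient not yet suspected of COVID-19 a poor match for a recipient. This is a good argument that *f* is small. It does not correct the entry rule for the pairs that remain.

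**The direction needs an asymmetry.** The protocol does not say that recipients are confirmed before transfusion, and any who were not would partly offset the effect. This stands as a condition on the conclusion.

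**Sensitivity analysis 1 narrows the window to ±7 days.** It caps the lag at 7 days, and in the main model the ratio then stays at or below 1.05 for shares up to 15%. It is offered for other reasons (rapid progression, out-of-network transfer) and keeps the same forward-looking rule. The Fine-Gray and intent-to-treat analyses add no confirmation-date condition.

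**A stronger reading to resist.** A reader might infer that plasma must look worse in every analysis. The documents do not support that. Discharge alive can move in plasma's favour, as shown, and ICU transfer and ventilation can both occur before the test, so comparators have no guaranteed event-free time for them. In the remdesivir subgroup, comparators already on that drug are unlikely to be unsuspected cases.

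**Conclusion.** The eligibility gap is real on the readable text: followed as written, it admits comparators selected on a test made after index, and no planned analysis removes them. The resulting bias is conditional. It applies only to comparators indexed before confirmation, and its direction for mortality assumes that recipients were confirmed before transfusion.

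Under the main model's assumed hazards the mortality ratio is raised by about 1-3% at a 2-5% share and 4-9% at 10-15%. Rises of 13-20% need 10-15% of comparators to have finished their stay before testing positive, which nothing in the documents supports. Fixed 14-day lags within the same stay would also give more (1.07 at 5%, 1.14 at 10%). At a 10% share with such lags, a true 0.70 would appear as about 0.80, a material part of the effect the study was sized for. With few such patients or short lags the effect is negligible. The count of affected patients decides which case applies, and the protocol does not ask for it.

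**What to change.** Make three changes before matching is run.

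1. Add to step 3, for both groups: a patient is eligible for a risk set only if a sample giving a positive RT-PCR was collected on or before the index date and the patient is alive and in a BSWH hospital on that date.
2. Add to the Figure 1 footnote: a stay that ended before the first positive sample was collected is not the COVID-19 admission.
3. Report, by group, how many patients the rule removes. If confirmation by index was always intended, the number will be zero and the text will say so.

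The cost is two sentences and one date filter on RT-PCR results that the study already uses to define its population. The comparator pool becomes slightly smaller, and any recipients transfused before a positive sample leave the main analysis.

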## Appendix 2. Baseline covariates

- Age (continuous)
- Race and ethnicity
- Site
- Comorbidities in the past 12 months including the index date unless specified
  - History of cancer
    - Hematopoietic
    - Solid tumor excluding non-melanoma skin cancer
    - Non-melanoma skin cancer
  - Cardiovascular conditions
    - Stroke
    - Thrombotic or thromboembolic complications including stroke, myocardial infarction, venous thromboembolism, deep vein thrombosis, and pulmonary embolism
    - Hypertension
    - Heart failure
    - Cardiac arrhythmias including ventricular tachycardia, ventricular fibrillation, atrial arrhythmia, and cardiac arrest
  - Chronic respiratory disease
    - Chronic obstructive pulmonary disease
    - Asthma
  - Diabetes
  - Chronic kidney disease 1-4
  - Chronic kidney disease 5 or end-stage renal disease
  - Chronic liver disease
  - History of organ transplantation
  - HIV
  
  - Obesity at admission
  - Sickle cell disease
- Pregnancy status (yes, no) from index date to study completion
- Comedications from hospital admission to the index date
  - Antiviral drugs
    - Remdesivir
    - Lopinavir/Ritonavir
    - Other HIV protease inhibitors.
  - Hydroxychloroquine/Chloroquine
  - Azithromycin
  - Glucocorticoid/Steroids
    - Dexamethasone
    - Prednisone
    - Hydrocortisone
    - Methylprednisolone
  - Anti-platelet agents
  - IL-6 inhibitor/antagonist
    - Tocilizumab
    - Sarilumab

- Siltuximab
  - ACE-Inhibitors (ACEi)/Angiotensin Receptor Blockers (ARBs)
  - Anti-thrombotic drugs
- Disease severity based on level of oxygenation support (Appendix 3) 4-12 hours prior to index
- Vital signs closest to the index date
  - Respiratory rate
  - Heart rate
  - Systolic blood pressure
  - Temperature
- Laboratory results closest to index date
  - Creatinine,
  - D-dimer
  - Cardiac troponin (TnI or TnT)
  - Absolute lymphocyte count
  - Ferritin
  - C-reactive protein

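### Days from first positive RT-PCR to the index date is an available, plausible confounder that is missing from the matching variables, the propensity score and the balance check

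*Protocol*

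**What the plan says.** **Matching (III. Study Design, Cohort Sampling, step 3).** Untreated patients are matched on calendar date ("Calendar date around the index date within" ±2 days), age within 5 years, sex and "Days from hospital admission to the index date". No tolerance is given for the last item.

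**What admission means (Figure 1 footnote).** "Hospital admission includes the earliest encounters at emergency or inpatient departments around COVID-19 confirmation within" ±14 days.

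**Propensity score (step 4).** "Baseline covariates for the propensity score modeling is listed below and further defined in Appendix 2". The list covers age, race and ethnicity, site, comorbidities, concomitant medications, laboratory results, vital signs and "Oxygen requirements as a proxy for disease severity (Appendix 3) 4-12 hours prior to the index date". Appendix 2 repeats these items in more detail and adds pregnancy. Neither list has an interval from RT-PCR or from symptom onset.

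**Balance check (IV, Comparative Analyses).** Absolute standardized differences are computed for each covariate, and those above 0.1 enter the Cox model.

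**Other uses of time.** Secondary Analyses item 3 would "stratify analyses by time interval from hospital admission to the index date", split at 72 hours. Sensitivity Analyses item 1 narrows the admission window to ±7 days because "COVID-19 could progress quickly" and because a wide window around confirmation could leave residual confounding by severity and survivor bias.

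**Recipient immunity (VI. Limitations).** The section on antibody titer says that patients' own antibody status is not accounted for.

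**The concern.** Time since diagnosis could plausibly be related both to the decision to transfuse and to the risk of death within 28 days. If so, it is a confounder of the primary hazard ratio. The design controls time since admission, and the wide admission window lets the two clocks drift apart.

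The protocol recognises the problem in its first sensitivity analysis. The remedy there is to restrict the cohort, not to adjust for the interval, and the primary analysis stays as it is. The planned safeguard against residual imbalance works only on listed covariates. A difference between the groups in time since the positive test would be neither displayed nor corrected.

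The date needed is already in hand: neither the ±14-day nor the ±7-day rule can be applied without the confirmation date, and Data Sources names the laboratory system that holds the test results.

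**Working it through.** No figure in the protocol quantifies this point. Table 1 (V. Sample Size) does not depend on it. That table reproduces within 0.005 in all 16 rows with Freedman's log-rank formula (for example 0.709 against the printed 0.71 for 1,000 patients at 1:1), and it would not change.

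**Step 1: is the interval in any list?**

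| Place | Time variable present | Time since RT-PCR |
|---|---|---|
| Cohort Sampling, step 3 | calendar date; days from admission | no |
| Cohort Sampling, step 4 | none | no |
| Appendix 2 | none as a covariate; look-back windows only | no |
| Secondary Analyses, item 3 | admission to index, <72 h or ≥72 h | no |
| Sensitivity Analyses, item 1 | admission to confirmation, as an eligibility limit | not adjusted for |

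**Step 2: how far can the two clocks separate?** Let A be days from admission to index and G be days from the RT-PCR to admission, negative when the test follows admission. Then days from RT-PCR to index are T = A + G. G lies between −14 and +14 in the main analysis and between −7 and +7 in the sensitivity analysis. A is taken as matched exactly.

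- For two patients with the same A, the largest possible difference in T is 14 − (−14) = 28 days in the main analysis and 7 − (−7) = 14 days in the sensitivity analysis.
- The protocol does not say that the positive test must precede the index date. If it must (an assumption), T cannot be below 0 and the range is 0 to A + 14, or 0 to A + 7:

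| A (days) | Main, ±14 | Sensitivity, ±7 |
|---|---|---|
| 2 | 0 to 16 | 0 to 9 |
| 3 | 0 to 17 | 0 to 10 |

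The sensitivity analysis reduces the spread but does not remove it.

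**Step 3: would the planned diagnostics show an imbalance?** The standardized differences are computed for the covariates on the list. T is not on it, so the 0.1 rule cannot be triggered by T.

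**Step 4: can the bias be sized?** That would need the distribution of T by exposure group and the relation of T to mortality after matching on everything else. The protocol gives neither, so no bias estimate follows from it.

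**The case against.** The strongest reply is that a match requires far more than equal time since admission. The propensity score includes oxygen support shortly before index, C-reactive protein, ferritin, D-dimer, lymphocyte count, vital signs, remdesivir and steroids. These describe the patient's current state, which is a likely route from disease stage to death. This stands: a reader might infer that patients at very different stages are simply treated as comparable, and the documents do not support that.

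The ranges above are also only limits. Because admission is the earliest emergency or inpatient encounter near confirmation, a patient who tests positive at such a visit has both clocks starting together. Long gaps arise mainly when the test and that first encounter were separate. How often that happens is not stated.

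A reader might want to attach a number. Suppose no true effect, 70% of treated and 50% of untreated patients in a lower-risk stage, and mortality of 20% and 30% in the two stages. The spurious risk ratio is (0.7×0.20 + 0.3×0.30)/(0.5×0.20 + 0.5×0.30) = 0.23/0.25 = 0.92. With 15% and 35% it is 0.21/0.25 = 0.84. Exchanging the two groups gives 0.25/0.23 = 1.09 and 0.25/0.21 = 1.19. Every input except the overall 25% mortality is invented. The calculation also assumes that the imbalance and the mortality contrast both survive matching on the variables above. It shows a mechanism and is no estimate for this study.

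Two further inferences go too far. Time since the test is not the only proxy for a recipient's antibody status: days from admission is another, and a test date records when testing happened, not when infection began. And if plasma works differently by stage, that is effect modification, which does not by itself bias the primary hazard ratio.

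Finally, Limitations already concedes residual confounding and lists bias analysis, negative outcome controls and E-values, if feasible. Step 4 also excludes covariates that are strongly related to treatment but only weakly to the primary outcome, and nothing in the protocol shows that this interval predicts death once severity is modelled. These points lower the expected size of the problem. They do not explain why a measured, pre-index candidate confounder is left off the list when the protocol itself names the wide window as a source of confounding.

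**Conclusion.** The point holds as a gap in the confounder set. Days from first positive RT-PCR to index is absent from matching, from the propensity score and from the balance check. Time since admission stands in for it only loosely, within eligibility limits of 0 to 16 days at day 2, or 0 to 9 under the ±7-day restriction, assuming the test precedes the index date. The protocol acknowledges the source of confounding but leaves the primary analysis unadjusted for it.

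The size and direction of any remaining bias are unknown, and the other covariates will absorb part of it. The protocol does not show that the primary hazard ratio is materially biased. The case for acting is that the variable is plausible, already available and cheap to include, and that without it the reader cannot see whether the groups differ.

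**What to change.** 1. In Cohort Sampling step 4 and in Appendix 2, add days from the first positive RT-PCR specimen to the index date, as a continuous variable in a flexible form such as a spline.
2. Include it in the standardized-difference check in Comparative Analyses, before and after matching, so that the 0.1 rule applies to it. If the step 4 selection rule later removes it from the propensity model, still report its balance.
3. Optional and exploratory: beside Secondary Analyses item 3, stratify by this interval if numbers allow. This addresses effect modification and is not needed to protect the primary estimate.

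The cost is one variable derived from dates the study already needs, a short wording change and possibly a few lost matches. Table 1 is unaffected. The test date remains an imperfect marker of infection onset, which deserves a sentence in Limitations.
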